PROTOCOL

Effect of Postoperative Oral Carbohydrate Administration in Total Knee Arthroplasty

Patients

October 16, 2022

Effect of Postoperative Oral Carbohydrate Administration in Total Knee Arthroplasty

1. Research background

In recent years, the concept of accelerated rehabilitation surgery (enhanced recovery after surgery, ERAS) has developed vigorously, using a series of optimized evidence-based medical support with preoperative, intraoperative and postoperative programs to reduce postoperative physiological and psychological stress trauma response, so as to achieve the goal of accelerating patient rehabilitation^[1]. Perioperative fasting water ban management is an important component of ERAS. Studies have found that prolonged preoperative drinking and fasting will increase the postoperative insulin resistance, cause hypertension, and increase the risk of postoperative infection, which is not conducive to the postoperative recovery of^[2]. Oral carbohydrates for at least 2h before anesthesia can reduce the perioperative stress response, improve patient comfort and satisfaction, and promote the postoperative rehabilitation of^[3]. The^[4] of the Chinese Expert Consensus and Path Management Guide for Accelerated Rehabilitation Surgery (2018 edition) advocates the early postoperative recovery of diet. Studies have shown that the early recovery of oral eating, drinking water and early oral assisted nutrition after elective abdominal surgery can promote the recovery of intestinal motor function, help to maintain intestinal mucosa function, prevent microflora imbalance and displacement, and can reduce the incidence of postoperative infection and shorten the postoperative hospitalization time by^[5]. At present, shortening the perioperative water fasting time needs to be concentrated in the preoperative stage. Although the guidelines and a small number of studies recommend the early recovery of diet after surgery, there is no clear stipulation on the recovery time of postoperative diet and drinking water, and most domestic hospitals still perform fasting for at least 6h after surgery.

Carbohydrates are perioperative good oral nutritional fluids. In recent years, studies have shown that preoperative oral carbohydrates can not only supplement the lost water and energy, improve their thirst and hunger, but also improve the postoperative metabolism and stress changes, reduce postoperative insulin resistance, shorten the hospital stay, and accelerate the^[6] recovery of patients compared with clear water. Furthermore, preoperative oral carbohydrate has been confirmed by many studies and does not increase the risk of reflux aspiration in^[7]. However, most of the current clinical studies of oral carbohydrate effects on postoperative recovery focus on the preoperative oral phase, and only a few small samples have shown that postoperative oral carbohydrate improves postoperative comfort^[8]. Therefore, further systematic studies on the effects of early postoperative oral carbohydrates on postoperative recovery remain lacking.

Directory of reference

[4] Surgery Branch of Chinese Medical Association, Anesthesiology Branch of Chinese Medical Society. Chinese Expert Consensus and Path Management Guidelines for Accelerating Rehabilitation Surgery (2018) [J]. *Chinese Journal of Anesthesiology*, 2018,38 (001): 8-13.

1.1 Study Purpose

1.1.1 Main study objective: To evaluate the effect of oral carbohydrates early after TKA on the nutritional status of elderly patients.

1.1.2 Secondary study objectives: To evaluate the effect of early oral carbohydrate administration on the comfort and safety of TKA in elderly patients.

1.2 Study endpoint

1.2.1 Primary study endpoints

Pre-albumin levels in venous blood in the fasting state on the day of surgery, 1d and 3d after surgery.

1.2.2 Secondary study endpoints

1.2.2.1, Effectiveness study endpoint

- 1) The level of retinol-binding protein in venous blood on the day and 1d and 3d after surgery;
- 2) The insulin resistance index in venous blood was checked on the empty stomach on the morning, 1d and 3d after the operation;
- 3) NRS score of thirst and hunger at 2h, 6h and 8h after surgery;
- 4) Abating distension within 24h after surgery;
- 5) The incidence of hypoxemia and reflux aspiration within 24h after surgery;
- 6) Time of anal exhaust for the first time after surgery;
- 7) Time to leave bed for the first time after surgery;
- 8) Length of hospitalization;
- 9) Postoperative subject satisfaction score.

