the PACU into two study groups: early carbohydrate feeding group (EOF group) and conventional feeding group (control group). Routine feeding group (Group C): Patients in group C were observed with 60min of abnormal vital signs after extubation, and returned to the ward for fasting and fasting for at least 6 h, and began to eat gradually through the mouth after anal exhaust. Early carbohydrate feeding group (EOF group): The EOF group drank 10.5% of 5 ml/kg body weight (100ml containing 12.5g maltodextrin, fructose and glucose) after extubation in the resuscitation room. PACU management: Patients will randomly enter the PACU into two study groups: early carbohydrate feeding group (EOF group) and conventional feeding group (control group). Routine feeding group (Group C): Patients in group C were observed with 60min of abnormal vital signs after extubation, and returned to the ward for fasting and fasting for at least 6 h, and began to eat gradually through the mouth after anal exhaust. Early carbohydrate feeding group (EOF group): The EOF group drank 10.5% of 5 ml/kg body weight (100ml containing 12.5g maltodextrin, fructose and glucose) after extubation in the resuscitation room.

To evaluate the drinking criteria for patients in the EOF group: Steward wake score of 6 and wake level level 3, take 5 ml/kg body weight of 12.5% carbohydrate (100ml containing 12.5g maltodextrin, fructose, and glucose) according to the patient's consent. The process of drinking carbohydrates was to take 30ml orally first. After observing the swallowing without abnormality, the patient was ordered to drink the remaining drinks within 2h. After the patient returned to the ward, the liquid diet began to gradually overenter the normal diet. When the patient was able to tolerate the normal diet, v.

Evaluation process of the drinking index:

1. Steward score: Akefulness: 0-no response to stimulus; 1-some response to stimulus; 2-full awake.(2) Respiratory tract patency degree: 0 points-the patient's respiratory tract needs support; 1 points-the patient's respiratory tract can maintain patency without support; 2 points-the patient can cough according to the doctor's guidance.(3) Body activity degree: 1 points-the patient's limb has no activity; 2 points-the patient's limb has an unconscious activity; 3 points-the patient's limb can carry out conscious activities

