3.1.3 The Follow-up Period

Record: Patients had fasting serum prealbumin, retinol-binding protein levels, and

insulin resistance index on the same day, 1 day and 3 days after surgery.

Record: 2 hours, 6 hours and 8 hours postoperative digital scores; bloating, hypoxemia and reflux aspiration occurred 24 hours after surgery.

Record: length of hospitalization, first anal exhaust time, first ambulation time, nausea and vomiting, and patient satisfaction.

4. Subject recruitment and protective measures

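### The 2 h thirst and hunger score can come before the EOF drink is finished, and no pre-drink score or record of intake is listed

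*Protocol*

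**What the plan says.** Comfort is part of the secondary objective (Protocol 1.1.2). Its most direct measure is item 3 of 1.2.2.1: "NRS score of thirst and hunger at 2h, 6h and 8h after surgery". The follow-up schedule in 3.1.3 repeats the times: "Record: 2 hours, 6 hours and 8 hours postoperative digital scores". I take these to be the same thirst and hunger ratings. Neither place lists a rating before the drink, and 3.1.3 lists no record of how much has been drunk.

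Section 3.1.2 gives the EOF sequence. The patient must first be extubated and reach "Steward wake score of 6 and wake level level 3". Then "The process of drinking carbohydrates was to take 30ml orally first", and next "After observing the swallowing without abnormality, the patient was ordered to drink the remaining drinks within 2h". The total is 5 ml/kg. A liquid diet follows on the ward.

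Controls are observed for 60 min after extubation and then "returned to the ward for fasting and fasting for at least 6 h, and began to eat gradually through the mouth after anal exhaust". Allocation is random, on entry to the PACU.

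**The concern.** The ratings are timed from surgery. The drink is timed from a recovery point that differs between patients and has no clock time. Whenever the wake criteria are met after surgery has ended, the permitted drinking period runs past the 2 h score. Two EOF patients who both follow the protocol can then be rated at 2 h, one with the drink finished and the other with little more than the test portion. With no record of volume, the analysis cannot tell them apart.

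The 2 h score is also the least mixed of the three on the EOF side. By 6 h and 8 h, EOF patients may be on the ward diet, so those scores reflect the drink plus later intake.

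Separately, without a pre-drink rating any differences in thirst and hunger already present in the PACU stay in the error term, and chance imbalance cannot be examined. An analysis plan written later cannot recover ratings or volumes that were never collected.

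**Working it through.** The protocol gives no figure of its own on this point, so there is none to reproduce. The check is timeline arithmetic.

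**Inputs from the protocol.** Score times 2, 6 and 8 h (1.2.2.1 item 3; 3.1.3). First portion 30 ml, remainder within 2 h after the swallow check, volume 5 ml/kg (3.1.2).

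**Assumptions.** Time from surgery to the start of the 2 h drinking allowance: t0 = 0.25 to 1 h. Body weight: 45 to 80 kg. Correlation between pre-drink and later rating: ρ = 0.3, 0.5 or 0.7. The documents give none of these.

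**Window and score times.** Latest permitted finish = t0 + 2 h. Share of the window elapsed at the 2 h score = (2 − t0)/2. Gap from latest finish to the 6 h score = 6 − (t0 + 2).

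| t0 (h) | Latest finish (h after surgery) | Share of window elapsed at 2 h | Gap to 6 h score (h) |
|---|---|---|---|
| 0.25 | 2.25 | 87.5% | 3.75 |
| 0.5 | 2.5 | 75% | 3.5 |
| 1 | 3 | 50% | 3 |

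Any t0 above zero puts the latest finish beyond 2 h, so the overlap itself needs no assumed figure. The assumption only sets its length. Even at t0 = 2 h the 6 h score would come 2 h after the window closes.

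**Least volume a compliant patient may have had at 2 h.** 30 ml / (5 ml/kg × weight):
- 45 kg: 30/225 = 13.3%
- 60 kg: 30/300 = 10.0%
- 70 kg: 30/350 = 8.6%
- 80 kg: 30/400 = 7.5%

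The upper end is 100%.

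**Value of a pre-drink rating.** With covariate adjustment the residual variance is multiplied by 1 − ρ²:
- ρ = 0.3: 0.91, so 9% removed
- ρ = 0.5: 0.75, so 25% removed
- ρ = 0.7: 0.51, so 49% removed

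**The case against.** The strongest reply is that the trial compares two assigned feeding strategies. A 2 h rating is a fair randomised comparison of early permitted drinking with continued fasting, and variable intake belongs to the strategy. That stands. The score is not invalid, but its meaning is unclear while nobody knows how much had been drunk. The 30 ml figure is also a worst case. The drink is given in the resuscitation room, so many patients may finish well before 2 h, and the documents give no typical value. Dilution is therefore probable, but its size is unknown.

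A reader might go further in four ways that the documents do not support.

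- *The whole comfort objective is tested at mixed stages of treatment.* Only one of three score times overlaps the drinking window, and satisfaction (item 9) is a further patient-reported measure.
- *The 6 h score catches some controls just after their first intake.* The start of the control fast is not defined. Read in sequence, it begins on return to the ward, about 1 h after extubation, so release would come no earlier than about 1 + 6 = 7 h after extubation. The research background describes usual practice as counted from surgery, which would put the earliest release at 6 h. Even then, eating also requires anal exhaust. It is a possibility under one reading, not a fact.
- *The missing baseline biases the comparison.* Patients are randomised, so it costs precision only. The gain rests wholly on an assumed correlation, and pre-operative fasting and the pre-operative drink are the same for everyone.
- *The 2 h allowance might run from surgery.* That would shrink the overlap to the boundary, but the text places it after the swallow check.

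**Conclusion.** The point holds for the 2 h score alone. Because that score and the drink run on different clocks, a compliant EOF patient can be rated with 30 ml to the full volume taken. With a start 0.25 to 1 h after surgery, the permitted window outlasts the score by 0.25 to 1 h. The likely effect is some dilution of the early contrast and difficulty in interpreting it. The comparison remains valid, and the 6 h and 8 h scores lie outside the window.

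The missing pre-drink rating is a loss of precision, worth 9 to 49% of the variance over the assumed correlations, with no bias. All sizes rest on the assumed start times, weights and correlations. This is a minor finding on one time point of a secondary endpoint, worth acting on because the remedy is cheap and the data cannot be recovered afterwards.

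**What to change.** In 1.2.2.1 item 3 and 3.1.3:

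1. Record thirst and hunger NRS in both arms in the PACU when the wake criteria are met, before any study drink and preferably before the patient is told the allocation. Use it as a covariate.
2. Record the drink start time and the volume taken by the 2 h score.
3. Either time the first post-drink score from the moment the wake criteria are met, in both arms, and place it after the drinking window has closed; or keep it at 2 h after surgery and state that it compares the strategies with the drink possibly incomplete.
4. Leave the 6 h and 8 h scores as they are, and record whether each control has had any intake by then. Moving them to the recovery clock would put the 6 h score at 6.25 to 7 h after surgery under the same assumptions, which could pass the earliest control release if the fast is counted from surgery.
5. State from what moment the control fast and the 2 h drinking allowance are each counted, so that 3.1.2 can be reconciled with the score times.

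These are measurement changes and leave every feeding and fasting rule as it is. The cost is one extra pair of 0 to 10 ratings, a note in both arms of when the wake criteria were met, and a few case report form fields. If the first score is moved, it will no longer fall at a round hour after surgery.

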1.2.2.2. Safety study endpoint

- 1) The incidence and severity of various adverse events (AE) from the start of oral carbohydrates to the end of the trial;
- 2) The incidence and severity of adverse events such as nausea, vomiting and hypoxemia from the first start of drug administration to the end of the trial;
- 3) Number of antiemetic drugs used within 24h after the first start to the first start of drug administration;

2. Expected results

Oral carbohydrates in the early postoperative period can improve patient nutritional

status, improve comfort and satisfaction without increasing the incidence of adverse events.

3. Design and method of the study

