3.1.2 Treatment Period

Actively control blood pressure, blood pressure and blood sugar, correct anaemia and hypoproteinemia, and increase protein intake before surgery. The dietary plan was informed by the ward nurse: all patients were fasted with solid food 6 hours before surgery and took 200 milliliters of carbohydrates orally 2-3 hours before surgery.

The venous access was open after home invasion and was routinely monitored electrocardiogram(ECG), non-invasive blood pressure(NBP) , oxygen saturation(SpO₂), bispectral index (BIS). Parecoxib 40 milligrams of analgesia was given intravenously at 30 minutes before the start of the procedure. Adductor canal block (ACB) and Infiltration between popliteal artery and capsule of knee (IPACK) block were performed on the lower limbs of the surgical side using an ultrasound high-frequency line array probe before induction of the general anesthesia procedure.

Anesthesia induction: after static injection of Midazolam 0.03 milligrams / kilogram, Propofol 2 milligrams / kilogram , Sufentanil 0.4 milligrams / kilogram, Cisatracurium 0.2 milligrams / kilogram. The tracheal tube was inserted after 3minutes and mechanical controlled ventilation was performed mechanical controlled ventilation, fraction of inspired oxygen (FiO₂) 40%, oxygen flow 2 litres/ minutes, minute ventilation 7 milliliters / kilogram, respiratory rate (RR) 12 times/ inspiration-to-expiratory ratio(I: E)1:2, maintain partial pressure of carbon dioxide in endexpiratory gas (PETCO₂) 35-40 millimeters of mercury (mmHg) . Anesthesia maintenance: intravenous propofol 4~7 milligrams / kilogram/ hour, remifentanil 0.3-0.5 microgrammes/kilogram/ hour, maintain BIS 40~60. A restrictive fluid management strategy was adopted, with 6ml/ kg·h supplemented with physiological needs, blood loss was supplemented with hydroxyethylstarch fluid, and concentrated red blood cells were infused at hemoglobin (Hb) <80 grams / litre to maintain patient blood pressure and heart rate fluctuations less than ±20% of the basal value . Dexamethasone 5mg and totoxetron 2mg for prophylactic antiemesis were given intravenously at 30min before the end of the surgery. All patients used hydromorphone patient-controlled intravenous analgesia (PCIA) pump for continuous: 1ml / h, automatic control: 5ml, locking: 10min, limit: 35ml / h, adjust parameters according to the pain.

Internal postanesthesia care unit (PACU) management: Patients will randomly enter

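### The adverse-event window in safety item 1 opens at an intake that, on the likelier reading, Group C never has, and items 2 and 3 are not tied to a post-randomisation time common to both groups

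*Protocol*

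**What the plan says.** Protocol section 1.2.2.2 lists three safety endpoints, each with its own counting window.

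- Item 1 covers "adverse events (AE) from the start of oral carbohydrates to the end of the trial".
- Item 2 covers "nausea, vomiting and hypoxemia from the first start of drug administration to the end of the trial".
- Item 3 is worded "Number of antiemetic drugs used within 24h after the first start to the first start of drug administration".

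No separate start is given for Group C, and the drug in items 2 and 3 is not identified.

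Section 3.1.2 sets the order of events. Before the operation, all patients "took 200 milliliters of carbohydrates orally 2-3 hours before surgery". Parecoxib follows 30 minutes before the procedure. Near the end, "Dexamethasone 5mg and totoxetron 2mg for prophylactic antiemesis were given intravenously at 30min before the end of the surgery". Allocation comes later: "Patients will randomly enter the PACU into two study groups". The EOF group then takes the carbohydrate drink after extubation, provided that the wakefulness criteria are met and the patient agrees. Group C is observed for 60 min after extubation, fasts for at least 6 h on the ward, and eats once flatus has passed.

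Section 2 expects benefit "without increasing the incidence of adverse events".

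**The concern.** A safety comparison needs the same counting period in both groups, opening at a time that every randomised patient reaches. Item 1 opens instead at receipt of the treatment. In a trial whose control is fasting, that event belongs to one group only, and within that group only to patients who are well enough and willing to drink.

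The protocol states this start itself, so it is not a detail left to the statistical analysis plan. An analysis plan that follows the protocol takes the problem over.

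At stake is the safety half of the expected conclusion. Safety is a secondary objective (section 1.1.2). The drink is given soon after extubation to patients aged 65 or over, so nausea, vomiting and antiemetic use in the first hours are what a reader will look at. If staff have to choose a start for Group C, the result depends partly on that choice.

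**Working it through.** The protocol gives no event rates and no figure to reproduce. The check is to place each possible start on the protocol's own timeline.

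**Inputs.** Preoperative drink 2-3 h before surgery, parecoxib 30 min before, prophylaxis 30 min before the end of surgery, randomisation at PACU entry, and Group C's 60 min of observation and at least 6 h of fasting (all section 3.1.2). Surgery lasting more than 3 h is excluded (section 4.2).

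**Possible starts**

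| Start | Does Group C have it? | Relative to randomisation |
|---|---|---|
| Study drink in the PACU | No | After |
| Preoperative 200 ml drink | Yes | Before |
| Parecoxib | Yes | Before |
| Antiemetic prophylaxis | Yes | Before |
| Hydromorphone pump | Yes | Start time not stated |

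Item 1 names oral carbohydrates, so only the first two rows can apply to it. Items 2 and 3 say drug administration, so all five are possible.

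**Item 1.** Section 1.1.1 states the objective as carbohydrate given early after the operation, and section 2 also speaks of the early postoperative period. That makes the study drink the likelier start. Group C then has no start for any patient. EOF patients who do not reach the drinking criteria, or who decline, have none either.

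**What happens if a start is improvised**

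- *Group C from first oral intake.* If the fasting period runs from return to the ward, the window opens at least 1 h + 6 h = 7 h after extubation. If the 6 h were counted from extubation, it would still be at least 6 h. Early nausea and vomiting are then counted in EOF but missed in Group C, which makes EOF look worse.
- *Group C from PACU entry, EOF from the drink.* EOF patients must first reach the wakefulness criteria. Nausea or hypoxemia before that point counts in Group C but not in EOF, which makes EOF look better.
- *Patients without a start left out.* Randomised EOF patients who never drank drop out of the safety count.

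The first two choices bias the comparison in opposite directions. The protocol does not say which applies.

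**Items 2 and 3.** If the drug is the study drink, the reasoning for item 1 applies unchanged. If it is something given before the operation, both groups open together but before allocation:

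- Preoperative drink: at most 3 + 3 = 6 h, and more than 2 h, before the end of surgery. Item 3's 24 h then reach from 24 - 6 = 18 h to just under 24 - 2 = 22 h after surgery.
- Parecoxib: at most 0.5 + 3 = 3.5 h before the end of surgery. Item 3 then reaches at least 24 - 3.5 = 20.5 h after surgery.

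In both cases the two prophylactic antiemetics lie inside the window. If the drug is the prophylaxis itself, the window opens 0.5 h before the end of surgery, again before randomisation. If it is the hydromorphone pump, the start cannot be placed.

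**The case against.** The strongest reply has four parts.

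**Items 2 and 3 need not mean a carbohydrate drink.** Parecoxib, the prophylaxis and the hydromorphone pump are described for both groups, and the last two do not come before induction. This stands. A reader might infer that all three items must either lack a start in Group C or open before induction. The document does not support that for items 2 and 3. What remains is that the protocol names none of these drugs as the start.

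**A preoperative start would leave the groups balanced.** This also stands. Adding the same prophylaxis to every patient leaves a difference in mean antiemetic counts unchanged, and the protocol does not say whether item 3 counts mandated prophylaxis at all. It would be wrong to infer a serious loss of information from that reading. The cost is a window that includes time before allocation and, for item 3, less than a full postoperative day.

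**The main aspiration risks are handled elsewhere.** Section 1.2.2.1 item 5 anchors hypoxemia and reflux aspiration to the 24 h after surgery for everyone. A reader might infer that these events have no valid comparator, and that is not so. Section 3.1.3 also lists nausea and vomiting without distinguishing the groups, but gives them neither a start nor a time limit, so it does not settle items 1 to 3.

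**Item 3's doubled start looks like a translation fault.** Agreed, and nothing here rests on it.

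**Conclusion.** The point holds in this form. Item 1, on its likelier reading, gives no start to any Group C patient or to EOF patients who never drink. The improvised alternatives give unequal windows, with a gap of at least 7 h after extubation in one case (taking the fast to begin on return to the ward). Items 2 and 3 have a start that is not tied to a time common to both groups after randomisation. They share item 1's defect only if the drug means the study drink.

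The size of any bias in event rates cannot be worked out from the document. It gives no rates, no time from PACU entry to the drink, and no expected share of EOF patients who will not drink. The conclusion rests on reading oral carbohydrates in item 1 as the postoperative drink. Sections 1.1.1 and 2 favour that reading, but section 1.2.2.2 does not state it.

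The prealbumin primary endpoint and the 24 h hypoxemia and reflux aspiration endpoint are untouched. This should be corrected, because the safety conclusion depends on it, but it is confined to secondary endpoints.

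**What to change.** In section 1.2.2.2, use one start for every randomised patient in both groups, whether or not the drink is taken.

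- Items 1 and 2: count from randomisation at PACU entry, or from the end of surgery as section 1.2.2.1 item 5 already does.
- Item 3: number of antiemetic drugs used within 24 h after that same time, excluding the intraoperative prophylaxis.

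Randomisation at PACU entry keeps the window wholly after allocation, but needs a recorded clock time and gives hypoxemia a different start from section 1.2.2.1. End of surgery matches that section, but includes a short interval before allocation, which is the same in kind for both groups. Either is acceptable, provided that one is chosen for all three items.

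The cost is three phrases and, for PACU entry, one time on the case report form. The downside is that the short interval before the drink counts in EOF, although the drink cannot have caused events in it. The matching interval counts in Group C too, so the comparison stays fair.
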